4.1. Protocol Deviations

Protocol deviations will be tracked by the study team throughout the conduct of the study in accordance with the Protocol Deviation Management Plan.

- Data will be reviewed prior to freezing the database to ensure all important deviations are captured and categorised on the protocol deviations dataset.
- The SI dataset will include all protocol deviations; the analysis dataset will include only important protocol deviations. The analysis dataset will be used for the listing of important protocol deviations.
- The study endpoints will be reported using the populations detailed in Section 4 of this document regardless of whether the participants deviate from the protocol.
- A separate listing of all inclusion/exclusion criteria deviations will also be provided. This listing will be based on data as recorded on the inclusion/exclusion page of the eCRF.

5. CONSIDERATIONS FOR DATA ANALYSES AND DATA HANDLING CONVENTIONS

5.1. Study Treatment & Sub-group Display Descriptors: Group 1

Treatment Group Descriptions			
RandAll NG		Data Displays for Reporting	
Code	Description	Description	Order in TLF
A	400 mcg IH oxytocin	400 mcg IH	1
B	10 I.U. IM oxytocin	17 mcg IM	2

The treatment dosage will be included in the footnotes for the respective tables/listings. If treatment codes have been displayed in the tables/listings the treatment descriptions should be included as footnotes.

5.2. Baseline Definitions

For all endpoints (except as noted in baseline definitions) the baseline value will be the latest pre-dose assessment with a non-missing value. If time is not collected, Day 1 assessments are assumed to be taken prior to first dose and used as baseline. Unscheduled visits will not be used for baseline calculation

Baseline definitions for Group 1

Parameter	Study Assessments Considered as Baseline			Baseline Used in Data Display
	Screening	Day -1	Day 1 (Pre-Dose)	
Safety				
Vital Signs (blood pressure, heart rate, temperature, respiratory rate)	X	X	X	Day 1
LAB	X			Screening

Unless otherwise stated, if baseline data is missing no derivation will be performed and baseline will be set to missing.

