8.2. POPULATION PHARMACOKINETIC (POPPK) ANALYSES

PK samples will be analysed periodically throughout the study duration to enable development of a preliminary population PK model. If appropriate, a population PK analysis may also be conducted on the final data. In addition the oxytocin plasma concentration-time data may be merged with historical data and analysed as part of a population PK meta-analysis. The timeline for these analyses will be independent of the analysis described in this RAP. To support this analysis a NONMEM-specific data file will be generated, the specifications of which are provided in POP PK RAP appendix.

8.3. Secondary Pharmacokinetic Analyses: Group 1

8.3.1. Endpoint / Variables : Group 1

- Cmax, Cp10, Cp20, Cp30, Area under the concentration-time curve from time zero (pre-dose) to three hours (h) (AUC[0-3h]) will be compared as data permit.

Due to sparse PK concentrations, it is not possible to include a formal statistical analysis to compare IH and IM Oxytocin therefore no statistical analysis will be performed.

8.4. Exploratory Pharmacodynamic Analyses: Group 1

8.4.1. Endpoint / Variables: Group 1

- Pre and post-delivery haemoglobin
- Questionnaire results from participants

8.4.2. Summary Measure: Group 1

Pre and post-delivery Haemoglobin will be summarized and listed along with other haematology parameters. A box plot will be produced for pre and post-delivery haemoglobin.

A listing and a summary table will be produced for the questionnaire results from the Rotahaler.

8.4.3. Population of Interest: Group 1

The exploratory analyses will be based on the Safety population, unless otherwise specified.

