10.2.1.1. Time & Events General Overview

Group 1

Procedure	Study Day			
	Screening ⁴	Main Phase	Follow – Up 1 (approx. 24 hours post dose)	Follow – Up 2 (7-14 days post dose)
Informed Consent and Demography	X			
Brief Physical Examination	X			
Medical history (incl. substance abuse)	X			
Inhaler device training / education session	X			
Laboratory assessments ¹	X			
Vital signs ²	X	X		
Pharmacokinetic blood sample		X		
Oxytocin Administration (IM/IH)		X		
Full blood count		X		
Labour Events Documentation		X		
Device acceptability questionnaire ³		X		
Prior / concomitant medication review	X	X	X	X
AE review		----- continuous review -----		
SAE review		----- continuous review -----		

1. Only required if done as part of routine care. Additional study-specific laboratory assessments not required.
2. Includes blood pressure, heart rate, temperature, respiratory rate
3. Only to be used when randomized to IH oxytocin
4. To be completed after 18th week of pregnancy (based on estimated date of delivery).

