10.2.1.2. Time & Events - Main Phase Procedures

Group 1

Procedure	Pre-dose	Time post dose										
		3 min	5 min	10 min	15 min	20 min	30 min	1 hr	2 hr	2.5 hr	3 hr	4 hr
Vital signs ¹							X		X			
Pharmacokinetic blood sample	X ²	X	X	X	X	X	X	X	X	X	X	X
Prior medication review	X											
Concomitant medication review		----- continuous review -----										
AE review		----- continuous review -----										
SAE Review		----- continuous review -----										
Device Acceptability Questionnaire ³												X
Full Blood Count	X											X

1. Includes blood pressure, heart rate, temperature, respiratory rate
2. Predose PK sample to be taken immediately prior to administration of study treatment
3. Only to be administered when randomized to IH oxytocin

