10.10.7. Safety Tables

Safety: Tables					
No.	Population	IDSL / Example Shell	Title	Programming Notes	Deliverable [Priority]
Adverse Events (AEs)					
3.17.	Safety	AE1	Summary of All Adverse Events by System Organ Class and Preferred Term		DR [1], SAC
3.18.	Safety	AE1	Summary of Drug-Related Adverse Events		DR [1], SAC
3.19.	Safety	AE1	Summary of Non-Serious Adverse Events		DR [1], SAC
3.20.	Safety	AE15	Summary of Common (>1 Subject) Non-serious Adverse Events by System Organ Class and Preferred Term (Number of Subjects and Occurrences)	FDAAA, EudraCT	DR [1], SAC
Serious and Other Significant Adverse Events					
3.21.	Safety	AE16	Summary of Serious Adverse Events by System Organ Class and Preferred Term (Number of Subjects and Occurrences)	FDAAA, EudraCT	DR [1], SAC
3.22.	Safety	AE1	Summary of Adverse Events Leading to Permanent Discontinuation of Study Drug or Withdrawal from Study		DR [1], SAC

Safety: Tables					
No.	Population	IDSL / Example Shell	Title	Programming Notes	Deliverable [Priority]
Laboratory: Hematology					
3.23.	Safety	LB1	Summary of Haematology Values		DR [1], SAC
3.24.	Safety	LB1	Summary of Haematology Changes from Baseline		DR [1], SAC
Vital Signs					
3.25.	Safety	VS1	Summary of Vital Signs		DR [1], SAC
3.26.	Safety	VS1	Summary of Change from Baseline for Vital Signs		DR [1], SAC
3.27.	Safety	VS7	Summary of Vital Sign Results Relative to Potential Clinical Importance (PCI) Criteria Post-Baseline Relative to Baseline		DR [1], SAC
Exploratory : Questionnaire Results					
3.28.	Safety	SAFE_T1	Summary of Device Acceptability Questionnaire for Rotahaler Inhaler		DR[1], SAC

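### Group 1 fixes the laboratory baseline at Screening although a pre-dose full blood count is scheduled, so the haematology change table (Table 3.24) does not isolate peripartum change

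*SAP*

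**What the plan says.** **Baseline.** Section 5.2 of the Group 1 RAP states: "For all endpoints (except as noted in baseline definitions) the baseline value will be the latest pre-dose assessment with a non-missing value". In the table beneath, under the column heading "Study Assessments Considered as Baseline", the laboratory row is marked at Screening only, and the display baseline is Screening. The vital-signs row is marked at Screening, Day -1 and Day 1, and uses Day 1. The section closes with: "Unless otherwise stated, if baseline data is missing no derivation will be performed and baseline will be set to missing".

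**Screening tests.** The general schedule (10.2.1.1) lists laboratory assessments at Screening with the footnote "Only required if done as part of routine care. Additional study-specific laboratory assessments not required". On the timing of Screening it says: "To be completed after 18th week of pregnancy (based on estimated date of delivery". Section 2.3 puts Screening within 168 days of the dosing session.

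**Scheduled counts.** The main-phase schedule (10.2.1.2) has its own row, "Full Blood Count", marked at pre-dose and at 4 h. The routine-care footnote is not attached to it.

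**Reporting.** Haemoglobin before and after delivery is the only endpoint for the exploratory pharmacodynamic objective (2.2). Section 8.4.2 says: "Pre and post-delivery Haemoglobin will be summarized and listed along with other haematology parameters", and adds a box plot. The display list includes Table 3.23 (values), Table 3.24 ("Summary of Haematology Changes from Baseline"), Figure 3.1 (the box plot) and Listing 49 (all haematology data).

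**Group 2.** Section 5.2 of the Group 2 RAP marks the laboratory row at all three times and uses Day 1.

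**The concern.** The exception replaces a scheduled measurement taken before dosing with an optional one that may be months old. A reader of Table 3.24 will take change from baseline to mean change over delivery and treatment. With a Screening baseline it also contains whatever happened to haemoglobin during the rest of the pregnancy, over an interval that differs from woman to woman.

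Because a missing baseline stops the derivation, a woman with both scheduled counts but no routine screening test drops out of the table. Those who stay are selected by local antenatal practice.

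The comparison of arms is descriptive. Randomisation would balance the earlier drift only in expectation, and each arm's own mean change stays distorted. The formal PK comparison has been withdrawn because so few samples were quantifiable (2.1, 3.1), so haemoglobin is one of the few Group 1 results left that bear on drug effect.

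**Working it through.** **1. The screening window.** Section 2.3 gives 168 days for Screening plus 7 to 14 days of follow-up, and states about 183 days in total. Check: 168 + 14 = 182, or 183 counting the dosing day. The stated figure reproduces. Also 168 / 7 = 24 weeks, which is week 18 to week 42 (week 42 as the upper end is an assumption). So 168 days is the intended maximum gap from Screening to dosing.

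**2. Interval covered by the change.** With the Screening baseline, the span to the last count is at most 168 × 24 + 4 = 4036 hours. With the pre-dose baseline, it runs from the pre-dose draw to 4 hours after dosing.

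**3. Which displays the laboratory row governs.** The Group 1 display list contains no chemistry or urinalysis table, figure or listing. The laboratory displays are Tables 3.23 and 3.24, Figure 3.1 and Listing 49, all haematology. Of these, only Table 3.24 is a change from baseline. The laboratory row therefore acts on Table 3.24.

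**4. What Table 3.24 estimates.** Write Hb for haemoglobin:

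Hb(4 h) − Hb(Screening) = [Hb(4 h) − Hb(pre-dose)] + [Hb(pre-dose) − Hb(Screening)]

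The first bracket is the change over the scheduled pair of counts, called peripartum change here. The second is drift before dosing. The document gives no value for either, so the following uses assumed values, with a peripartum change of -10 g/L:

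| Assumed drift, Screening to pre-dose (g/L) | Change shown in Table 3.24 (g/L) |
|---|---|
| -5 | -15 |
| 0 | -10 |
| +5 | -5 |
| +10 | 0 |

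The error in each woman's change equals her drift, whatever the true peripartum change.

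**5. Loss of women.** The number contributing is 10 × (1 − fraction without a screening test) per 10 women. For assumed fractions of 10%, 30% and 50% this gives 9, 7 and 5, even if all 10 have both scheduled counts. The document does not give the actual fraction.

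**The case against.** **There is no contradiction.** The general rule allows for exceptions noted in the table, and the laboratory row is one. This stands. The fault is a poorly chosen exception.

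**The laboratory row may not be meant for the full blood count.** The schedule separates laboratory assessments from the full blood count, so the general rule could be said to govern the latter. This fails on the display list: with no other Group 1 laboratory display planned, the row would have nothing to act on.

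**The endpoint is a pair of values, not a change.** A reader might infer that the only pharmacodynamic endpoint is lost. The document does not support that. Section 8.4.2 plans values, a listing and a box plot, and Table 3.23, Figure 3.1 and Listing 49 need no baseline. What remains is that these show distributions or individual records, and Table 3.24 is the only planned summary of within-woman change.

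**The change could be recovered.** If the table shell prints change at both pre-dose and 4 h, subtracting the two means gives the peripartum mean. The shell's content is not shown. The subtraction would give no spread, and would cover only women with a screening test.

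**Variability.** A reader might infer that the Screening baseline makes the change noisier by a definite factor. With equal variances, the ratio of standard deviations is √[(1 − r_Screening) / (1 − r_pre-dose)], where r is the correlation with the 4 h value. The document gives no correlations. Assumed pairs (Screening, pre-dose) of (0.5, 0.6) give 1.12, and equal correlations give 1.0. No factor can be claimed.

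**Flags in Listing 49.** A reader might expect the clinical-importance flags to change too. They would not, because the change-from-baseline limits for haemoglobin and haematocrit in Group 1 section 10.8.1 are blank.

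**Pre-dose may not mean pre-delivery.** Nothing in the document equates the two or times the pre-dose count against delivery; the footnote requiring sampling immediately before dosing covers the PK sample only. This stands as a limit on interpretation, but pre-dose is still the closest scheduled count before treatment.

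**Conclusion.** The point holds for Table 3.24. As written, the Group 1 change table measures 4 h minus an optional screening value that may be up to 168 days old. It therefore mixes earlier drift with peripartum change and omits women without a screening test. The plan's own general rule and the Group 2 choice both point to the pre-dose value.

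Neither the size nor the direction of the distortion can be derived from the document. The figures above are illustrations on assumed drift and assumed missingness. The 168 days is a maximum, so a mid-pregnancy baseline is possible but not stated to be typical.

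The conclusion assumes that the scheduled pre-dose counts were taken, and that Table 3.24 follows the laboratory row of section 5.2. The table is descriptive, haemoglobin is exploratory, and no hypothesis is tested, so no primary or secondary conclusion changes. This is a should-fix.

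**What to change.** In section 5.2 of the Group 1 RAP, set the haematology baseline for Table 3.24 to the Day 1 pre-dose full blood count. Identify it by its nominal pre-dose time point: both counts surround a single dose, and section 5.2 treats untimed Day 1 assessments as pre-dose. State whether Screening may be used as a fallback when the pre-dose count is missing and, if so, that such values are flagged.

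The cost is one row of the baseline table and a sentence on the fallback. No new data or displays are needed. Table 3.23, Figure 3.1 and Listing 49 can stay as they are.

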2.2. Study Objective(s) and Endpoint(s)

Group 1 – Women in Third Stage of Labour (TSL)op

Objectives	Endpoints
Primary Objectives	Primary Endpoints

 To characterize the pharmacokinetics of single doses of IH oxytocin and 10 International Units (I.U.) IM oxytocin in women in TSL. 	
 Plasma concentration time profile for IH oxytocin and 10 I.U. IM oxytocin. PK parameters: Maximum observed plasma concentration (C_{max}), Observed plasma concentrations at 10 minutes (min) postdose (C_{p10}), Observed plasma concentrations at 20 min post-dose (C_{p20}), Observed plasma concentrations at 30 min post-dose (C_{p30}), Time to C_{max} (t_{max}), Area under concentration-time curve (AUC), and Terminal phase half-life (t_{1/2}) will be calculated as data permit.
Secondary Objectives	Secondary Endpoints

 To evaluate the safety and tolerability of inhaled oxytocin. 	
 General safety parameters: adverse events (AE); absolute values and changes over time of vital signs (blood pressure, heart rate, respiratory rate, temperature).

Objectives	Endpoints

 To compare pharmacokinetics of IH oxytocin to 10 I.U. IM oxytocin in women in TSL. 	
 C_{max}, C_{p10}, C_{p20}, C_{p30}, Area under the concentration-time curve from time zero (pre-dose) to three hours (h) (AUC[0-3h]) will be compared as data permit.
Exploratory Objectives	Exploratory Endpoints

 Pharmacodynamic effect of IH oxytocin and 10 I.U. IM oxytocin in women in TSL. 	
 Pre and post-delivery haemoglobin

 Participant feedback regarding ease of use, instructions, and perceived ability of patients to use the ROTAHALER. 	
 Questionnaire results from participants.

[figure not shown]
[figure not shown]
Group 2 – Non-pregnant, non-lactating females of child bearing potential

Objectives	Endpoints
Primary Objectives	Primary Endpoints

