10.2.1.2. Time & Events - Main Phase Procedures

Group 2 - Sessions 1 and 2

Procedure	Pre-dose	Time Post Dose														
		2 min	3 min	5 min	8 min	10 min	15 min	20 min	30 min	45 min	1 hr	1.5 hr	2 hr	2.5 hr	3 hr	4 hr
Brief Physical Exam	X															
Pregnancy Test	X															
Alcohol Breath Test, Smokerlyzer, Urine Drug Screen ¹	X															
Vital signs ²	X			X			X		X		X					X
12-lead ECG	X	X				X		X	X		X					X
Cardiac Telemetry		-----Continuous-----														
Spirometry ³	X											X				
Pharmacokinetic blood sample	X ⁵	X	X	X	X	X	X	X	X	X	X	X	X	X	X	X
Immunogenicity Sample	X															
Laboratory assessments (including liver chemistries)	X															X
Prior medication review	X															
Concomitant medication review		-----continuous review-----														
AE review		-----continuous review-----														
SAE Review		-----continuous review-----														
Discharge from unit ⁴																X

1. Smokerlyzer at Principal Investigator (PI)/designee discretion if smoking history in question.
2. Includes blood pressure, heart rate, temperature, respiratory rate, and SpO2
3. FEV 1.0 will be performed in triplicate at each time point. Record all three values on source document, and record best effort in eCRF.
4. Discharge at PI discretion, no sooner than 4-hours post-dose.
5. 3 pre-dose samples: approximately 1 hr pre-dose, 30 minutes pre-dose, and 15 minutes pre-dose

CONFIDENTIAL

205920

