10.6. Appendix 6: Derived and Transformed Data

10.6.1. General

Multiple Measurements at One Analysis Time Point

 • Mean of the measurements will be calculated and used in any derivation of summary statistics but if listed, all data will be presented. • Participants having both High and Low values for Normal Ranges at any post-baseline visit for safety parameters will be counted in both the High and Low categories of “Any visit post-baseline” row of related summary tables. This will also be applicable to relevant Potential Clinical Importance summary tables.
Study Day

 • Calculated as the number of days from First Dose Date: 
 • Ref Date = Missing → Study Day = Missing • Ref Date < First Dose Date → Study Day = Ref Date – First Dose Date • Ref Date ≥ First Dose Date → Study Day = Ref Date – (First Dose Date) + 1

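### The Day 1 baseline does not fit either schedule: Group 1 has no pre-dose vital signs on the dosing day, and the Group 2 crossover has no session-specific baseline

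*SAP*

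**What the plan says.** **Group 1 RAP.** The general rule in Section 5.2 is that "the baseline value will be the latest pre-dose assessment with a non-missing value", except where the baseline table notes otherwise. The table row for vital signs marks Screening, Day -1 and Day 1 (pre-dose) as eligible, and gives Day 1 as the baseline used in displays. Two more rules follow: "If time is not collected, Day 1 assessments are assumed to be taken prior to first dose and used as baseline", and "if baseline data is missing no derivation will be performed and baseline will be set to missing" unless otherwise stated. Unscheduled visits are barred from baseline. The secondary safety endpoint in Section 2.2 covers "absolute values and changes over time of vital signs (blood pressure, heart rate, respiratory rate, temperature"). It is reported in Table 3.26 (change from baseline) and Table 3.27 (potential clinical importance relative to baseline).

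**Group 2 RAP.** Section 5.2 repeats the general rule and the untimed-Day-1 sentence. It gives Day 1 as the displayed baseline for vital signs, laboratory values, ECG and FEV1. Section 10.6.1 defines Study Day as "Calculated as the number of days from First Dose Date". The main-phase schedule in Section 10.2.1.2 is headed "Group 2 - Sessions 1 and 2" and includes pre-dose vital signs, ECG, spirometry and laboratory samples. The primary safety endpoint in Section 2.2 includes changes in vital signs and ECG parameters from pre-dose values.

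**The concern.** In Group 1 the table names a baseline that the RAP's own schedule never collects. Two programmers could both follow Section 5.2 and deliver different versions of Tables 3.26 and 3.27: one without change values, the other with changes from a reading taken months earlier in pregnancy but headed Day 1.

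In Group 2 every participant has two dosing sessions, but the baseline is tied to a single day. If that day is session 1, every session 2 change in vital signs and laboratory values is measured across days, although a same-day pre-dose value exists. Section 10.4.2 of the same RAP assigns adverse events by period, so the period structure was recognised there but not carried into the baseline.

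**Working it through.** **Group 1: which vital-sign readings exist?** The general overview (Section 10.2.1.1) has columns for Screening, Main Phase and two follow-ups, with no Day -1 visit. Vital signs are marked at Screening and in the Main Phase. The main-phase table (Section 10.2.1.2) has 12 time columns:

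- Vital signs: 12 cells, marked at 30 min and 2 h only.
- PK sample: 12 cells, all marked, including pre-dose.
- Full blood count: 12 cells, marked at pre-dose and 4 h.

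The PK and blood-count rows fill the pre-dose cell, so the blank in the vital-sign row is not a column shift. Scheduled Day 1 pre-dose vital-sign readings: 0. Scheduled Day 1 post-dose readings: 2.

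**Group 1: what Section 5.2 then yields.**

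1. Day 1 taken strictly, as a noted exception to the general rule: baseline is missing, nothing is derived, and Tables 3.26 and 3.27 have no baseline.
2. Latest pre-dose value, with Screening eligible: the tables are filled from Screening. Section 2.3 allows Screening up to 168 days before dosing, which is 168 / 7 = 24 weeks.
3. Untimed Day 1 readings, if there are any: they count as pre-dose, but the only scheduled Day 1 readings are post-dose.

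The RAP does not choose among these.

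**Group 2: which day is session 2?** Study Day = reference date − first dose date + 1. Section 2.3 puts session 2 between 48 hours (2 days) and 14 days after session 1:

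- earliest: 2 + 1 = Day 3
- latest: 14 + 1 = Day 15

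Day 1 is therefore session 1, and a literal Day 1 baseline precedes the session 2 dose by 2 to 14 days. The vital-sign row (16 cells for 16 columns) is marked at pre-dose, 5, 15 and 30 min, 1 h and 4 h in each session, so session 2 has its own pre-dose value.

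**Group 2: size of the added variation.** Assume equal variance σ² at every reading. A change between two readings with correlation ρ has variance 2σ²(1 − ρ). With within-session correlation w and between-session correlation b:

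SD ratio (session 1 baseline / own baseline) = √[(1 − b) / (1 − w)]

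Neither w nor b is in the documents, so these are assumed values:

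- b = w: 1.0
- w = 0.8, b = 0.7: √(0.3 / 0.2) = 1.22
- w = 0.8, b = 0.5: √(0.5 / 0.2) = 1.58
- w = 0.9, b = 0.7: √(0.3 / 0.1) = 1.73
- w = 0.9, b = 0.5: √(0.5 / 0.1) = 2.24

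**The case against.** The strongest reply for Group 1 is that the lead rule already resolves it: the latest non-missing pre-dose value applies, Screening is marked eligible, and so the tables are populated. That stands against any claim that they must be empty. It does not explain why the display column says Day 1.

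A reader might also infer that a 30 min post-dose value will become the baseline and cancel the effect being measured. The documents do not support that as an expected outcome. The rule operates only if time is not collected, the scheduled readings carry planned times, and Section 10.5.2 shows planned and actual times in listings. It is a contingent risk that is easily closed.

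For Group 2, the general rule could be read session by session, the endpoint wording points the same way, and Section 5.2 does not cite the Study Day formula. So the comparison with session 1 is the literal reading, not a certainty. Session 1 results are unaffected on any reading.

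A reader might further infer that drift or carry-over is charged to one treatment. Order is randomised in the crossover, so the documents do not show a systematic shift against either treatment; added variation is the supportable consequence.

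It is also fair that the safety tables are descriptive and no formal hypotheses are tested. The vital-sign limits for potential clinical importance are absolute, so a post-dose value is classified the same whatever the baseline. Finally, the Group 2 list of displays titles no table as change from baseline for ECG or spirometry (Tables 3.11 to 3.13). The baseline problem therefore reaches the listed change tables for chemistry, haematology and vital signs.

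**Conclusion.** The point holds as a conflict in Group 1 and an unfixed definition in Group 2.

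Group 1: the displayed vital-sign baseline is a reading that the schedule does not contain. The outcome is either no baseline or a Screening value up to 168 days old labelled Day 1. This rests only on the RAP's own tables. It does not extend to Group 1 haematology, whose stated baseline is Screening.

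Group 2: nothing makes the baseline session-specific, and the literal reading takes session 2 changes from a value 2 to 14 days earlier. The SD of those changes would be between 1.0 and about 2.2 times that obtained with the session's own baseline, depending on correlations that had to be assumed.

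That the tables will certainly be empty or wrong is not established. The correction is worth making because these changes are a secondary endpoint in Group 1 and part of a primary endpoint in Group 2.

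**What to change.** **Group 1 RAP, Section 5.2.** Set the vital-sign baseline used in displays to Screening, the latest pre-dose value in the schedule. Label it so in Tables 3.26 and 3.27, with a caution on the long interval to dosing. State that the untimed-Day-1 assumption does not apply to vital signs, because their scheduled Day 1 readings are all post-dose.

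**Group 2 RAP, Section 5.2.** Define baseline as the last pre-dose value of the same session, and apply it to the change tables for chemistry (3.8), haematology (3.10) and vital signs (3.15). State that ECG change from the same session's pre-dose value is displayed, since it is part of the primary endpoint and no listed title shows it. The standard shell behind Table 3.13 may already include it, but the RAP does not say so.

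**Cost.** Edits to two baseline tables, the derivation code and some labels, plus an ECG change display if the shell lacks one. No new data are needed. The one drawback is that a Group 1 change from Screening can span up to 24 weeks, hence the caution.

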10.5.2. Reporting Standards

General	

 The current GSK Integrated Data Standards Library (IDSL) will be applied for reporting, unless otherwise stated (IDSL Standards Location: https://spope.gsk.com/sites/IDSLLibrary/SitePages/Home.aspx): 
 4.03 to 4.23: General Principles 5.01 to 5.08: Principles Related to Data Listings 6.01 to 6.11: Principles Related to Summary Tables 7.01 to 7.13: Principles Related to Graphics 	
Formats	

 All data will be reported according to the actual treatment the subject received unless otherwise stated. GSK IDSL Statistical Principles (5.03 & 6.06.3) for decimal places (DP's) will be adopted for reporting of data based on the raw data collected, unless otherwise stated. Numeric data will be reported at the precision collected on the eCRF. The reported precision from non eCRF sources will follow the IDSL statistical principles but may be adjusted to a clinically interpretable number of DP's. 	
Planned and Actual Time	

 Reporting for tables, figures and formal statistical analyses: 
 Planned time relative to dosing will be used in figures, summaries, statistical analyses and calculation of any derived parameters, unless otherwise stated. The impact of any major deviation from the planned assessment times and/or scheduled visit days on the analyses and interpretation of the results will be assessed as appropriate. Reporting for Data Listings: 
 Planned and actual time relative to study drug dosing will be shown in listings (Refer to IDSL Statistical Principle 5.05.1). Unscheduled or unplanned readings will be presented within the subject's listings. 	
Unscheduled Visits	

 Unscheduled visits will not be included in summary tables and/or figures. All unscheduled visits will be included in listings. 	

Descriptive Summary Statistics	
Continuous Data	Refer to IDSL Statistical Principle 6.06.1
Categorical Data	N, n, frequency, %
Reporting of Pharmacokinetic Concentration Data	
Descriptive Summary Statistics	Refer to IDSL Statistical Principle 6.06.1 Assign zero to NQ values (Refer to GUI_51487 for further details)
Reporting of Pharmacokinetic Parameters	
Summary table	Summary table will be produced as described in Section 8.1.2
Listing	All PK Parameters that are collected will be listed

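### Both RAPs deem untimed Day 1 records pre-dose, but Day 1 is the dosing day and most or all scheduled Day 1 vital signs are post-dose, so a post-dose value can be stored as baseline

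*SAP*

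**What the plan says.** The general rule in Section 5.2 of both RAPs is that "the baseline value will be the latest pre-dose assessment with a non-missing value". It opens with "For all endpoints (except as noted in baseline definitions", so it yields to the parameter table beneath it. It then adds: "If time is not collected, Day 1 assessments are assumed to be taken prior to first dose and used as baseline".

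The parameter tables name the baseline used in displays:
- **Group 1 RAP:** Day 1 for vital signs. The laboratory row reads "LAB X Screening". There is no ECG row.
- **Group 2 RAP:** Day 1 for vital signs, laboratory tests, ECG and FEV1.

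In both tables the column for Day 1 carries a pre-dose qualifier.

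Section 10.5.2 of both RAPs has a separate rule on timing: "Planned time relative to dosing will be used in figures, summaries, statistical analyses and calculation of any derived parameters, unless otherwise stated". Appendix 3 of each applies no assessment windows.

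**The concern.** The assumption is harmless where Day 1 holds only pre-dose assessments. Here the dose is given on Day 1, and every scheduled main-phase safety measurement falls within 4 h of it. A dosing-day record without a clock time is therefore often, and for Group 1 vital signs always on the extracted schedule, a post-dose record. The rule nevertheless deems it pre-dose.

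At stake are the change-from-baseline tables and the vital-sign tables that set post-baseline results against baseline using the limits of potential clinical importance. Safety is a primary objective in Group 2, where the endpoints include changes in vital signs and ECG parameters from pre-dose values. It is a secondary objective in Group 1.

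**Working it through.** **1. How many scheduled dosing-day measurements are post-dose?** The inputs are the main-phase schedules (Section 10.2.1.2 of each RAP) and the baseline tables (Section 5.2). Share = post-dose marks / all marks.

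| Group | Assessment | Pre-dose | Post-dose | Share post-dose | Displayed baseline |
|---|---|---|---|---|---|
| 1 | Vital signs | 0 | 2 (30 min, 2 h) | 2/2 | Day 1 |
| 1 | Full blood count | 1 | 1 (4 h) | 1/2 | Screening |
| 1 | ECG | 0 | 0 | none | no row |
| 2, per session | Vital signs | 1 | 5 (5, 15, 30 min, 1, 4 h) | 5/6 | Day 1 |
| 2, per session | ECG | 1 | 6 (2, 10, 20, 30 min, 1, 4 h) | 6/7 | Day 1 |
| 2, per session | Laboratory | 1 | 1 (4 h) | 1/2 | Day 1 |
| 2, per session | Spirometry | 1 | 1 (1.5 h) | 1/2 | Day 1 |

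Group 2 sessions are at least 48 h apart (Section 2.3) and study day counts from first dose (Section 10.6.1). Session 2 is therefore not Day 1, and the rule reaches session 1 only.

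**2. Does another rule clearly prevent the error?**
- The planned-time rule in 10.5.2 gives way where something else is stated. Section 5.2 can be read as such a statement, and no text says that the planned label prevails.
- The pre-dose qualifier on the Day 1 column limits which records are eligible. But the disputed sentence deems an untimed record to be pre-dose, so the qualifier does not clearly exclude it.
- Study phases (Section 10.4.1) go by date. In Group 1 a record on the dosing date is On-Treatment, while 5.2 calls an untimed one pre-dose. In Group 2 the treatment start date satisfies both the Pre-Treatment and the On-Treatment definition.

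**3. Which displays use the baseline?**
- **Group 1:** Tables 3.26 (vital-sign change) and 3.27 (vital signs against the clinical-importance limits).
- **Group 2:** Tables 3.8 and 3.10 (chemistry and haematology change), 3.15 and 3.16 (vital signs).
- **Group 2 ECG and spirometry:** the listed tables are 3.11 to 3.13, and none is titled change from baseline. A wrong baseline could be stored, but the effect on a listed table is not shown.

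**4. Size for one record.** Change = value − baseline, so each of that woman's changes is off by true baseline − stored baseline. The values below are assumed for illustration, in Group 2: pre-dose systolic pressure 120 mmHg, an untimed 5-min reading of 90, and a 30-min reading of 115.
- True baseline: 90 − 120 = −30 and 115 − 120 = −5.
- Untimed reading stored as baseline: 90 − 90 = 0 and 115 − 90 = +25.
- Error in each: 120 − 90 = 30 mmHg.

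A post-dose systolic value under the 85 mmHg limit, if stored as baseline, would likewise count as abnormal at baseline and not after dosing.

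**5. Group 1 vital signs.** The general overview (Section 10.2.1.1) has vital signs at Screening and in the main phase, with no Day -1 visit. On the extracted schedule no Day 1 pre-dose reading exists, although Day 1 is the displayed baseline. The untimed-record sentence could then fill that gap with a 30-min or 2-h value.

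**The case against.** The strongest reply is that Section 5.2, read as a whole, already excludes post-dose records. The general rule defers to a table whose Day 1 column is pre-dose only, and derivations use planned time. A reading labelled 5 min or 30 min would then never qualify. The sentence also speaks of time not being collected, which most naturally means that no time field exists, and the plan treats blank fields separately as missing data. Finally, a record without a clock time can hardly be ranked as the latest except by its planned label, and that label would show it to be post-dose.

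Much of this stands. A careful programmer would probably use the planned label, so the error is less likely than the bare sentence suggests, and the plan does not settle which value would win. The reply does not remove the problem. The sentence positively assigns untimed Day 1 records to pre-dose, makes no exception for a post-dose label, and sits beside a planned-time rule that yields to contrary statements. If an assessment has no time field, all its Day 1 records are untimed and only the label can separate them.

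A reader might infer more: that untimed post-dose values certainly become baseline, that blood tests and ECGs are affected in both groups, or that a genuine pre-dose reading is displaced in Group 1. The documents support none of these. The outcome depends on how the sentence is programmed. Group 1 laboratory baseline is Screening and Group 1 schedules no ECG. Its extracted schedule has no Day 1 pre-dose vital sign to displace.

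**Conclusion.** The rule does not fit a design in which the dose and all main-phase safety readings share a day, and it should be changed. An untimed post-dose value **can** be stored as baseline for vital signs in both groups, and for laboratory tests, ECG and spirometry in Group 2 session 1. The tables open to distortion are 3.26 and 3.27 in Group 1 and 3.8, 3.10, 3.15 and 3.16 in Group 2.

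Per record, the error is the full difference between the true and the stored baseline. The total effect cannot be computed: the plan does not say how many records lack a time, and it may be none. The conclusion rests on the literal reading of Section 5.2. The Group 1 part also rests on the schedule as extracted by machine, so the absent pre-dose mark for vital signs should be checked against the original table.

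**What to change.** Replace the sentence in Section 5.2 of both RAPs with:

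*If clock time is not available, classify the record by its planned time point; a record with a post-dose planned time is never baseline; a record with neither is listed but not used as baseline.*

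In the Group 1 RAP, also reconcile the displayed vital-sign baseline of Day 1 with the main-phase schedule, which as extracted marks no pre-dose vital signs on the dosing day.

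The cost is one sentence in each RAP plus one check of the Group 1 table. No new data are needed, since Section 10.5.2 already has planned and actual times shown in the listings.
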